#### 9.2.2 Serious Adverse Events

An AE or SAE reaction is considered "serious" if, in the view of either the investigator or sponsor, it results in any of the following outcomes:

- Death
- A life-threatening adverse event\*

- Inpatient hospitalization or prolongation of existing hospitalization
- A persistent or significant incapacity or substantial disruption of the ability to conduct normal life functions
- A congenital anomaly/birth defect.
- Important medical events that may not result in death, be life-threatening, or require hospitalizations may be considered serious when, based upon appropriate medical judgment they may jeopardize the participant and may require medical or surgical intervention to prevent one of the outcomes listed in this definition. Examples of such medical events include allergic bronchospasm requiring intensive treatment in an emergency room or at home, blood dyscrasias or convulsions that do not result in inpatient hospitalization, or the development of drug dependency or drugabuse.
- \*Life-threatening adverse event. An AE is considered "life-threatening" if, in the view of either the investigator or sponsor, its occurrence places the participant at immediate risk of death. It does not include an AE that, had it occurred in a more severe form, might have caused death.

All SAEs will be:

- Recorded on the appropriate SAE form and CRF
- Followed through resolution by a study physician
- Reviewed and evaluated by the study chairs, relevant IRBs, and the DSMB
- 9.2.3 Procedures to be followed in the Event of Abnormal Laboratory Test Values or Abnormal Clinical Findings

The site principal investigator or appropriate sub-investigator is responsible for reporting all AE/SAEs that are observed or reported during the study, regardless of their relationship to study product. AE/SAEs, abnormal laboratory values, or abnormal clinical findings will be documented, reported, and followed appropriately.

For grading abnormal gynaecological events, refer to Appendix B, Division of AIDS Table for Grading the Severity of Adult and Pediatric Adverse Events, December 2004; Addendum 1: Female Genital Grading Table for Use in Microbicide Studies, November 2007.

For grading abnormal laboratory and clinical events, refer to Appendix C, DAIDS Toxicity Table for Grading the Severity of Adult and Pediatric Adverse Events, Version 2.1 July 2017.

# 9.3 Reporting Procedures

## 9.3.1 Serious Adverse Events

AEs will be followed until resolution even if this extends beyond the study- reporting period. Resolution of an AE is defined as the return to pretreatment status or stabilization of the condition with the expectation that it will remain chronic.

Any AE that meets a protocol-defined serious criterion must be submitted immediately (within 24 hours of site awareness) on an SAE form to the following address:

#### **BIOMEDICAL RESEARCH ETHICS COMMITTEE (BREC)**

University of KwaZulu-Natal (UKZN) Research Office, Westville Campus [name] Durban 4000 KZN, SOUTH AFRICA [contact] Email: [contact]

Any AE that meets a protocol-defined serious criterion must also be submitted within 7 days of site awareness) on an SAE form to the following address:

Chief Executive Officer South African Health Products Regulatory Authority Clinical Trials Unit [name] Pretoria [contact]

Other supporting documentation of the event may be requested by the study sponsor or the DSMB and should be provided as soon as possible.

The medical monitor and clinical protocol manager will be notified of the SAE by the site. The medical monitor will review and assess the SAE for regulatory reporting and potential impact on study subject safety and protocol conduct.

At any time during the study, if the investigator becomes aware of an SAE that is suspected to be related to study product, the investigator will report the event to the IRB at UKZN, UCSF and the Ragon Institute of MGH, MIT and Harvard.

#### 9.3.2 Regulatory Reporting

Following notification from the site principal investigator or appropriate subinvestigator, the study sponsor, will report any suspected adverse reaction that is both serious and unexpected. UCSF will report an AE as a suspected adverse reaction only if there is evidence to suggest a causal relationship between the drug and the AE. UCSF will notify SAHPRA in a safety report of potential serious risks from clinical trials or any other source, as soon as possible, but in no case later than 15 calendar days after the sponsor determines that the information qualifies for reporting as specified in 21 CFR Part 312.32. UCSF will also notify SAHPRA of any unexpected fatal or life- threatening suspected adverse reaction as soon as possible, but in no case later than 7 calendar days after the sponsor's initial receipt of the information. Relevant follow-up information to a safety report will be submitted as soon as the information is available. Upon request from SAHPRA, UCSF will submit to SAHPRA any additional data or information that the agency deems necessary, as soon as possible, but in no case later than 15 calendar days after receiving the request.

#### 9.3.3 Reporting of Pregnancy

Pregnancies occurring in study participants will be reported on the Pregnancy Report form. Efforts will be made to follow all pregnancies reported during the course of the study to pregnancy outcome pending the participant's permission.

# 9.4 Type and Duration of Follow-up of Subjects after Adverse Events

AEs and SAEs will be followed from the time of study treatment through resolution even if this extends beyond the study-reporting period. Resolution of an AE/SAE is defined as the return to pretreatment status or stabilization of the condition with the expectation that it will remain chronic.

Follow-up procedures, evaluations, and outcomes will be recorded on the appropriate data collection form.

# 9.5 Halting Rules

Study enrolment and dosing will be halted and an ad hoc DSMB review will be performed if any of the following occur at any time during the study:

- 1) One or more participants experience a treatment-related SAE.
- 2) Two or more participants experience treatment-related vulvar and/or vaginal ulceration, abscess, or necrosis.
- 3) Two or more participants experience a treatment-related severe (Grade 3) or life-threatening (Grade 4) systemic adverse event.
- 4) An overall pattern of symptomatic, clinical, or laboratory events that the monitor or DSMB consider associated with study product and that may collectively represent a serious potential concern for safety.

A decision to reinitiate the study and proceed with study treatments will be made based on the recommendation of the DSMB.

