#### 2.6 Potential Risks and Benefits

#### 2.6.1 Potential Risks

#### 2.6.1.1 Biological Risks: LACTIN-V and Placebo

The study product contains a naturally occurring strain of *L. crispatus* CTV-05. To date, there has been considerable amount of experience using LACTIN-V at concentrations up to  $2 \times 10^9$  cfu/dose without any apparent related adverse effects, with the exception of a short duration of asymptomatic vaginal discharge. No serious adverse events have been reported in Protocol No. LV-001, LV-002 and LV-004 using LACTIN-V at 5 x 10^6 and 5 x 10^8 cfu/dose, and no subject left the protocol due to an adverse event. No severe or severe-related adverse event has been experienced by more than one subject. In Protocol No. LV-003, using LACTIN-V at 5 x 10^8 cfu/dose, one subject in the placebo group experienced three simultaneous SAEs unrelated to LACTIN-V. Two subjects in the LACTIN-V group discontinued study treatment due to AEs; one subject became pregnant and the other reported nausea and diarrhea, which required treatment.

Safety results of the recently completed Phase 2a trial (LV-006) assessed colonization efficiency, safety, tolerability and acceptability of LACTIN-V at 2 x 10^9 cfu/ dose in 24 women with BV. No Grade 3 AEs or SAEs were observed during the clinical phase of the study. Based on the DAIDS Toxicity Table Addendum for Vaginal Microbicide Studies (November 2007)  designed to standardize AE assessment, a total of 120 total AEs were reported, 108 (90%) of which were Grade 1 and 12 (10.0%) were Grade 2 severity. The most common genitourinary AEs included vaginal discharge of study product (46%), abdominal pain (46%) and dysuria (21%). AEs were evenly distributed between LACTIN-V and placebo groups. All enrolled women (n=24) reported at least one AE. A single participant receiving placebo discontinued herself from study product due to a moderate AE (vaginal irritation).

Risks from the administration of LACTIN-V are low since colonization with this type of organism is strongly associated with improved vaginal health. No systemic risks are anticipated since this is an organism that is applied topically and not expected to be absorbed. These risks will be explained in the written informed consent form. No pregnant women, fetuses, prisoners, children, persons with an active STI or women undergoing in vitro fertilization are included in this study.

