Adverse effects that may be associated with LACTIN-V include those seen with other vaginally administered products, and include:

Most likely:

• Vaginal, genital or menstrual symptoms: vaginal discharge

Less likely:

- Gastrointestinal symptoms: abdominal (stomach area) pain, constipation, diarrhea, nausea, vomiting
- Urinary symptoms: needing to urinate urgently, needing to urinate at night and pain with urination

- Vaginal, genital or menstrual symptoms: genital itching, bleeding between
- menstrual periods, delayed menstrual periods, vaginal odor, vaginal burning sensation, vaginal irritation, vaginal bleeding, vaginal dryness, genital swelling, rash, vaginal candidiasis (yeast infection)
- Other symptoms: lower back pain

Rare but potentially life-threatening:

• Allergic reaction (including anaphylaxis) to the study product

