## 11.4 Safety Analysis

This study will be monitored for safety and to determine if any of the safety halting rules described in detail in Section 9.5 are met (one or more treatment-related SAE, two or more treatment-related vaginal ulceration, two or more treatment-related severe Grade 3 systemic adverse events). Thus, all patients will be evaluated for toxicity. The DSMB will review interim analyses comparing product-related AEs between the two treatment arms will be performed after half of the 60 participants complete the Follow-Up Study Visit 11, and then annually. Reports of these analyses will be sent to the Principal Investigator or Senior Investigators at the participating institutions.

The table below gives the probability of observing at least one incidence of AE together with the corresponding true AE rate for a total of 60 participants.

True AE rate:	0.5%	1%	2%	5%
P [AE>1]:	0.26	0.45	0.70	0.95

For example, the probability of observing at least one incidence of AE with true rate of 5% is 0.95.

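### Halting rule 3 gives a fixed two-participant count only to systemic Grade 3-4 events; related, non-serious Grade 3 genitourinary events outside rule 2 depend on discretionary rule 4

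*Combined protocol and SAP*

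**What the plan says.** Section 9.5 lists four conditions. Any of them, at any time, halts enrolment and dosing and calls an ad hoc DSMB review.

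- Rule 1: one participant with a treatment-related SAE.
- Rule 2: "Two or more participants experience treatment-related vulvar and/or vaginal ulceration, abscess, or necrosis".
- Rule 3: "Two or more participants experience a treatment-related severe (Grade 3) or life-threatening (Grade 4) systemic adverse event".
- Rule 4: "An overall pattern of symptomatic, clinical, or laboratory events that the monitor or DSMB consider associated with study product", where the events may together amount to a serious safety concern. It carries no number.

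Section 11.4 summarises the third rule as "two or more treatment-related severe Grade 3 systemic adverse events", so the limit to systemic events appears twice. The same section promises "interim analyses comparing product-related AEs between the two treatment arms" once half of the 60 women have completed Visit 11 (Day 36).

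On expected harm, section 2.6.1.1 states: "No systemic risks are anticipated since this is an organism that is applied topically and not expected to be absorbed". The same section's list of possible effects is largely genital and urinary. Its one rare, potentially life-threatening entry is "Allergic reaction (including anaphylaxis) to the study product".

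**The concern.** The fixed Grade 3-4 count applies where the protocol expects least harm and leaves out the site of application. Two women with related Grade 3 systemic events stop the trial by count. Two women with related Grade 3 genital or urinary events, not judged serious and not in rule 2, stop it only if someone judges that they form a pattern. Twice-weekly AE checks and individual discontinuation (sections 4.0 and 5.3.3.1) protect each woman but set no count across women. Safety is one of the three primary objectives, so a predictable response to repeated severe local events is worth having.

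**Working it through.** **1. What the fixed rules already catch.** This sets section 9.5 beside the female genital grading table in Appendix B.

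- Grade 3 vulvar rash, vulvar or vaginal lesions, vaginal lacerations and Bartholin's or Skene's abscess are all tied to hospitalization. If related, they would normally be SAEs under section 9.2.2, and rule 1 halts on one.
- Vulvar or vaginal ulceration, abscess or necrosis of any grade falls under rule 2.
- Vulvovaginitis and cervicitis add nothing separate. The composite is Grade 3 only when a component sign is Grade 3 by itself.

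**2. What is left without a count.** These Grade 3 events can occur without hospitalization: pain needing narcotic medication, severe tenderness, weeping vulvar edema, inability to void because of pain, PID with diffuse tenderness, and Grade 3 abnormal bleeding. Some may be judged serious under section 9.2.2, for example as substantial disruption of normal life functions, and then rule 1 applies.

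**3. The plan's own safety figures.** Section 11.4 gives the chance of at least one AE among 60 women as 0.26, 0.45, 0.70 and 0.95 at true rates of 0.5%, 1%, 2% and 5%. The formula 1 − (1 − p)^60 gives 0.260, 0.453, 0.702 and 0.954, so the table reproduces. The plan gives no such figures for the halting rules.

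**4. Chance of two or more cases.** The documents give no rate for this subset, so p is assumed, using the rates in the section 11.4 table. The formula is P(X ≥ 2) = 1 − (1 − p)^n − n·p·(1 − p)^(n−1). For n = 40 and p = 1%: 1 − 0.6690 − 0.2703 = 0.0607.

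| True rate | 20 LACTIN-V women (expected share of the 30 at the mid-trial review) | 40 LACTIN-V women | All 60, same rate in both arms |
|---|---|---|---|
| 0.5% | 0.4% | 1.7% | 3.7% |
| 1% | 1.7% | 6.1% | 12% |
| 2% | 6.0% | 19% | 34% |
| 5% | 26% | 60% | 81% |

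Among 40 women the chance reaches 50% only at a true rate of 4.2%. Under the present text, the chance that a fixed count of these non-serious events halts the trial is zero at every rate.

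**5. What earlier data say about p.** LV-005 and LV-006 had no Grade 3 or 4 AE (section 2.4). LV-006 had 18 LACTIN-V women. LV-005 randomized 12 women 3:1, taken here as 9 on LACTIN-V. One-sided 95% upper bounds are 1 − 0.05^(1/18) = 15.3% and, for both trials together, 1 − 0.05^(1/27) = 10.5%. These are ceilings for any Grade 3-4 AE, not estimates for this smaller subset. For LV-001, LV-002 and LV-004, at lower doses, section 2.6.1.1 adds: "No severe or severe-related adverse event has been experienced by more than one subject". The low rows of the table are the more plausible ones.

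**6. What a halt would cost.** Planned accrual is 60 in 65 weeks (Protocol Summary), or 60 in 75 weeks, or 3 per month (section 11.3): 0.923, 0.800 or 0.690 women per week. Dosing runs from Day 8 to Day 32, which is 24/7 weeks. So 3.2, 2.7 or 2.4 women are in dosing at any time, and two thirds of these (2.1, 1.8 or 1.6) are on LACTIN-V. Exact two-sided Fisher power for 20 against 40 women, 10% against 50%, is 89.1%, in line with the plan's statement of more than 88%. If two of the 40 LACTIN-V women lost all benefit (10% response instead of 50%), power would be 86.0%.

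**The case against.** The strongest reply is that the structure is deliberate. Rule 2 covers local harm through visible tissue damage at any grade, rule 3 covers systemic harm, and softer local complaints are left to judgement. Pelvic examinations themselves cause discomfort and slight bleeding (section 2.6.1.3). AEs were evenly spread between arms in earlier trials, and the one AE discontinuation in LV-006 was vaginal irritation in a placebo user. Staff are blinded, so a raw count would include placebo women, whereas the arm comparison in section 11.4 can separate product from applicator effects. Rule 3 as written also has a purpose, given the rare allergic reaction.

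Much of this stands. The uncounted set is small, the rates are assumed, and the DSMB charter, which is not in the documents, may set local counts. But subjective grading, clinician-judged relatedness and inclusion of placebo women apply equally to the systemic events that rule 3 already counts. They do not explain why local events of the same grade are left out.

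Two stronger readings are tempting, and the documents do not support them. A reader might infer that local harm has no halting rule; rules 1 and 2 show otherwise. A reader might also infer that nothing could stop the trial for these events before the mid-trial review. That review falls about 38 to 49 weeks after first enrolment (30 divided by the weekly accrual, plus 5 weeks: 37.5, 42.5 or 48.5). But rule 4 can be invoked at any time, by the monitor as well as the DSMB, and once invoked the halt is mandatory. The missing element is a fixed count, not a route to a halt.

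**Conclusion.** The point holds in a narrow form and at low severity. Related Grade 3 genitourinary events that are neither SAEs nor covered by rule 2 have no fixed trigger, while systemic events of the same grade do, in a trial of a topical product.

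The size rests on assumed rates. At 1% to 2%, the widened rule would be reached with probability 6% to 19% among 40 LACTIN-V women, or 12% to 34% if all 60 share the rate. The 26% and 60% figures need a 5% rate, which earlier trials do not rule out but nothing in the documents supports. They should not be read as a forecast.

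A reader might also infer that leaving the cervix out of rule 2 is an error of the same kind. That is debatable. Appendix B stops visible cervical lesions at Grade 2, and cytobrush sampling is another possible source of them. A grade limit or a sampling exclusion for the cervix would not match that rule's any-grade trigger. Adding the cervix is optional and forms no part of this conclusion.

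**What to change.** In rule 3 of section 9.5, replace *systemic adverse event* with *adverse event, systemic or local genitourinary*. Keep two or more participants, treatment-related, Grade 3 or 4. Do not count postcoital bleeding that is Grade 3 only because it follows more than 75% of coital acts, since a single act with bleeding would meet that criterion. Align the summary in section 11.4 and carry the wording into the DSMB charter.

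The cost is a short edit and no new examination. The downside is the higher chance of a temporary halt given above. A halt is reversible on the DSMB's recommendation (section 9.5). The two or three women in dosing at that moment could miss doses before Day 36. A further 0.7 to 0.9 women (weekly accrual times one week) would be taking metronidazole. They could pass the 48-hour limit in section 7.3 and be withdrawn, but section 5.3.1 replaces women lost before randomization. A few screened women could also pass the 30-day window from the FRESH Week 5 visit, and section 7.1.1 offers no rescreening to ineligible volunteers.

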## 9.6 Safety Oversight (DSMB)

Safety oversight will be under the direction of a DSMB, consisting of 3 voting members. The DSMB will meet once - prior to first enrollment, once - after half of the 60 participants complete the Follow-Up Study Visit 11(Day 36), and then, finally – once, after study conclusion and database lock, to assess safety and efficacy data in each arm of the study.

The DSMB will review aggregate safety data for increased rate of occurrence of serious suspected adverse reactions. If halting rules are initiated, more frequent meetings may be held. The DMSB will operate under the rules of an approved charter that will be written at the organizational meeting of the DSMB. At this time, each data element that the DSMB needs to assess will be clearly defined. The DSMB will advise UKZN, UCSF and the Ragon Institute at MGH of its findings.

# **10.0 MONITORING**

# 10.1 Site Monitoring Plan

Site monitoring is conducted to ensure that the human subject protections, study and laboratory procedures, study intervention administration, and data collection processes are of high quality and meet sponsor, ICH/GCP guidelines and applicable regulations, and that the study is conducted in accordance with the protocol, protocol-specific MOP and applicable sponsor standard operating procedures. The sponsoring agency, or its designee will conduct site-monitoring visits as detailed in the clinical monitoring plan.

Site visits will be made at standard intervals as defined by the sponsor and may be made more frequently as directed by the sponsor. Monitoring visits will include, but are not limited to, review of regulatory files, accountability records, CRFs, informed consent forms, medical and laboratory reports, and protocol and GCP compliance. Site monitors will have access to the study site, study personnel, and all study documentation according to the sponsorapproved site monitoring plan. Study monitors will meet with site principal investigators to discuss any problems and actions to be taken and document visit findings and discussions.

# **11.0 STATISTICAL CONSIDERATIONS**

# 11.1 Introduction

This is a Phase 2 randomized double-blind placebo-controlled trial to assess the impact of the live biotherapeutic product LACTIN-V containing *Lactobacillus crispatus* CTV-05 on the non-l*actobacillus* dominant microbiome of young women in South Africa at high risk of HIV acquisition.

The study plans to enrol and randomize 60 sexually experienced women age 18 to 23 years, who are using a reliable method of long- acting injectable birth control or are of nonchildbearing potential (permanently sterile). After enrolment, women will start a standard 7 day course of oral Metronidazole tablets. After completing the 7-day course of Metronidazole, subjects will be randomized to receive either placebo or LACTIN-V in a 1:2 ratio. The participants will receive protocol treatment for four weeks and will have four weeks of additional off treatment follow-up time.

# 11.2 Study Objectives and Outcome Measures

As described in section 3.2 and 3.3, the primary study objectives are to compare LACTIN-V with placebo following a 7-day treatment course with Metronidazole with respect to safety and impact on the vaginal microbiome, specifically *lactobacillus* growth and decrease in pro-inflammatory cytokines and HIV target cells.

In Objective 1, the outcomes of interest will be:

(1) a decrease in genital tract inflammation from baseline (the FRESH Study Visit before enrollment) to Day 36 Follow-Up Visit, as defined by a  $\geq$ 1 Log10 decrease in the concentration of cytokines that have been associated with an increased risk for HIV infection., and

(2) the change in the concentration of cytokines at the Final Visit on Day 64 (4 weeks after dosing phase completed) compared to baseline, number of endocervical CD4+ HIV target cells at Day 36 Follow-Up and Day 64 Final Visits compared to baseline, and in vitro anti-HIV activity of cervicovaginal lavage at Day 36 Follow-Up and Day 64 Final Visits. We will compare each outcome by study arm.

In Objective 2, the outcomes of interest will be:

(1) the presence of *Lactobacillus*-dominant vaginal microbial cervicotypes at the Day 36 Follow-Up Visit, and following the post-dosing phase at the Day 64 Final Visit in the LACTIN-V arm; and

(2) the comparison of *L. crispatus* vs. *L. iners* prevalence between treatment groups, quantity of vaginal *L. crispatus*, presence of the specific CTV-05 *L. crispatus* strain, persistence of colonization after stopping therapy, effect of sex and/or vaginal hygiene practices on colonization by lactobacilli, and stability of vaginal microbial communities over time in the treatment vs. placebo arms.

In Objective 3, the outcomes of interest will be:

- (1) the proportion of treatment related adverse events study arm, in particular Grade 3 AEs; and
- (2) the proportion of participants finding the product acceptable and are willing to use it Page 64 of 124

should it become commercially available, as measured in a standardized acceptability questionnaire.

